### 761 **7.3.1.2 Analysis of Type of Edema in Eyes that Progressed**

762 For eyes with OCT central subfield  $\geq 250$  microns at 16 weeks, the type of edema to which the  
763 eye progressed will be evaluated based on the reading center grading of FAs. The distribution of  
764 the type of edema will be provided.  
765

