## 218 **1.2 Study Objectives**

219 The objective of the study is to determine the incidence of progression to center-involved  
220 macular edema 16 weeks after cataract surgery in eyes with diabetic retinopathy and without  
221 definite center-involved DME. The incidence rates will be determined separately for each of the  
222 following subgroups:

223

224 1. Eyes in which no injection for DME was received recently prior to surgery or at the time  
225 of surgery\*, each to be further stratified by whether or not there was a history of any  
226 other prior treatment for DME:

227

a) No center involved DME and no non-center involved DME (i.e. no DME)

228

- *(central subfield [CSF]<190 for women or CSF<210 for men, and all inner subfields [ISF]<260, and all outer subfields [OSF]<220)*

229

b) No center involved DME and definite/uncertain non-center involved DME

231

- *(CSF <190 for women or CSF<210 for men, and at least 1 ISF  $\geq$ 260 or OSF $\geq$ 220)*

232

c) Uncertain center involved DME and no non-center involved DME

233

- *(CSF 190 to 249 for women or CSF 210 to 249 for men, and all ISF <260, and all OSF<220)*

234

d) Uncertain center involved DME and definite/uncertain non-center involved DME

237

- *(CSF 190 to 249 for women or CSF 210 to 249 for men, and at least 1 ISF  $\geq$ 260 or OSF $\geq$ 220)*

238

239 2. Eyes with an injection for DME received recently prior to surgery or at the time of  
240 surgery\*, stratified by whether the treatment was corticosteroids or anti-VEGF therapy.

241

242 \* Intravitreal or peribulbar corticosteroids within the last 4 months prior to surgery or on the day  
243 of surgery; anti-VEGF therapy within the last 2 months prior to surgery or on the day of surgery.

244

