## 333 H. Schedule of Study Visits and Examination Procedures

334

	Enrollment	0	4w+1w	16w+2w
Cataract Surgery		X		
E-ETDRS best corrected VA a	X		X	X
OCT b	X		X	X
Fluorescein angiography c				X
Eye Exam d	X		X	X
HbA1c e	X			

335 A medical history will be elicited at enrollment and an updated history at each visit. a= both eyes at each visit; includes protocol  
 336 refraction in study eye at each follow-up visit and in both eyes at enrollment.  
 337

338 b=study eye only; also obtained prior to the first non-topical DME treatment

339 c= obtained prior to the first non-topical DME treatment or at 16w if central subfield thickness  $\geq 250\mu$  and treatment for DME  
 340 (other than topical treatment) has not already been given.

341 d= study eye only at baseline and follow-up visits.

342 e=does not need to be repeated if HbA1c and lab normal values are available from within the prior 12 weeks and can be  
 343 performed within 3 weeks after enrollment.  
 344  
 345

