### 4.2 Testing Procedures

The following procedures will be performed at each protocol visit unless otherwise specified. All of the testing procedures do not need to be performed on the same day, provided that they are completed within the time window of a visit and prior to initiating any treatment.

Testing procedures at unscheduled visits are at investigator discretion. However, procedures that are performed should follow the standard DRCRnet protocol for each procedure.

1. E- ETDRS visual acuity testing in each eye (best corrected).
  - A protocol refraction in the study eye is required at all protocol visits. Refraction in the nonstudy eye is not required. When a refraction is not performed, i.e. at unscheduled visits, the most-recently performed refraction is used for the testing.
  - If the E-ETDRS visual acuity letter score is 0, then counting fingers, hand motion, and light perception are assessed.
2. OCT on the study eye
  - OCTs may only be graded by the reading center if determined likely to need manual grading
3. Ocular exam on study eye including slit lamp examination and dilated fundus examination.
4. Fluorescein angiography
  - Obtained at 16 week visit for all study eyes if OCT CSF  $\geq 250$  microns and treatment for DME (other than topical treatments) has not been given. If FA is to be obtained based on this criterion, the eye will be classified by the investigator as one of the following:
    - (1) **CME Only:** Presence of post-surgical CME as defined below, without the presence of DME.  
Post-surgical CME is defined as the presence of ALL of the following:
      - a. CSF  $\geq 250$  microns on OCT

562 **CHAPTER 5.**  
563 **MISCELLANEOUS CONSIDERATIONS IN FOLLOW-UP**

564  
565 **5.1 Complications of Cataract Surgery**

566 Complications of cataract surgery are managed by the cataract surgeon as judged indicated.  
567

568 **5.2 Treatment of Macular Edema in Nonstudy Eye**

569 Treatment of DME in the nonstudy eye is at investigator discretion.  
570

571 **5.3 Diabetes Management**

572 Diabetes management is left to the subject's medical care provider.  
573

574 **5.4 Subject Withdrawal and Losses to Follow-up**

575 A subject has the right to withdraw from the study at any time. If a subject is considering  
576 withdrawal from the study, the principal investigator should personally speak to the subject about  
577 the reasons, and every effort should be made to accommodate the subject.  
578

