### 7.2 Sample Size

703 Recruitment is planned for a period of up to 24 months. Distribution of enrolled eyes in the  
704 predefined subgroups as listed in section 7.1 will be evaluated after 6 months and a  
705 determination will be made at that time whether to continue or stop enrollment.

706  
707 A maximum of 100 eyes in the subgroup with no center involved DME and no non-center  
708 involved DME (group 1a; with/without prior treatment for DME) will be enrolled. Once this  
709 goal is met, recruitment may be stopped in this subgroup. Overall, a maximum of 500 subjects  
710 will be enrolled with no restriction on the number per site.

713 If the rate of progression is 5% in each of these groups (and if N=50 with prior treatment group  
 714 and N=50 without prior treatment group), the half width of the confidence intervals would be  
 715 around 6% with this sample size.  
 716

Proportion progressed to edema	Half-width of 2-sided 95% CI		
	N=50	N=75	N=100
0.05	0.06	0.05	0.04
0.10	0.08	0.07	0.06

717  
 718 **7.3 Statistical Analysis Plan**

719 **7.3.1 Primary Outcome**

720 **7.3.1.1 Primary Analysis**

721 As stated in section 7.1, the primary objective of the study is to determine the incidence of  
 722 progression to center-involved diabetic macular edema (DME) 16 weeks after cataract surgery in  
 723 eyes with diabetic retinopathy and without definite center-involved DME. The incidence rates  
 724 at the 16 week time point will be determined separately for each of the predefined subgroups as  
 725 listed in section 7.1. Progression to edema will be defined separately according to the predefined  
 726 subgroup, as detailed below. Point estimates and 95% confidence intervals will be evaluated for  
 727 each. Similar analyses will be conducted at the 4-week visit.  
 728

729 Within each of the subgroups of eyes with no center involved DME and no non-center involved  
 730 DME (group 1a; one subgroup with prior treatment for DME and one subgroup without prior  
 731 treatment for DME), the following will be evaluated:

- 732 a. Proportion of eyes that progressed to definite center involved edema, defined as  
 733 meeting any of the following criteria:  
 734 (1) OCT central subfield thickness  $\geq 250$  microns at 16 weeks and increased at  
 735 least 1 log OCT unit from baseline to 16 weeks  
 736 (2) Increased at least 2 log units from baseline to 16 weeks  

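### The edema-type analysis in 7.3.1.2 selects eyes by 16-week thickness rather than by progression, and 7.1 and 7.3.1.1 call an any-cause edema outcome DME

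*Protocol*

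**What the plan says.** Section 7.3.1.2 of the protocol carries the title "Analysis of Type of Edema in Eyes that Progressed". Its text takes eyes with CSF of at least 250 "microns at 16 weeks, the type of edema to which the" eye progressed is then evaluated from the reading center's FA grading. It states no change from baseline and has no clause for treated eyes.

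Section 7.3.1.1, definition (a), counts an eye as progressed to center-involved edema on any of three criteria:
- (1) 16-week CSF of at least 250 microns together with a rise of at "least 1 log OCT unit from baseline to 16 weeks";
- (2) "Increased at least 2 log units from baseline to 16 weeks", with no 250-micron floor;
- (3) non-topical treatment for DME or CME after surgery, with (1) or (2) already met before that treatment.

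On imaging, section 4.1 requires OCT and FA before the first non-topical treatment for DME or CME. Section 4.2 adds a 16-week FA only if CSF is at least 250 and "treatment for DME (other than topical treatments) has not been given". Footnote c of the schedule (1.3 H) has the FA "obtained prior to the first non-topical DME treatment or at 16w if central subfield thickness" reaches 250 microns, and so names DME treatment only.

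On the outcome label, section 1.2 opens "The objective of the study is to determine the incidence of progression to center-involved" and continues with macular edema, not qualified as diabetic. Section 7.3.1.1 gives the objective as the incidence of "progression to center-involved diabetic macular edema (DME) 16 weeks after cataract surgery in" eyes with diabetic retinopathy, and 7.1 says the same.

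**The concern.** The protocol's background separates DME from post-surgical CME, and section 1.1.5 makes the frequency of each type a stated aim. The primary outcome does not separate them: it is thickening on OCT, or treatment for either condition. The type distribution in 7.3.1.2 is the analysis that should say what the primary events were. If it is drawn from a different set of eyes, it cannot be laid over the incidence figures.

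The direction of selection also matters. Treatment is at the discretion of the surgeon and the investigator. A treated eye is dropped if its retina thins below 250 microns and kept if it does not. If one type responds to treatment more readily than the other, the reported mix shifts for that reason alone. A DME label on the outcome in two places then invites a reading of the incidence that the definition does not support.

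**Working it through.** **Primary figures.** The only precision figures in the protocol are the half-widths in 7.2. Using 1.96 × √(p(1−p)/n):
- p = 0.05, n = 50, 75, 100: 0.0604, 0.0493, 0.0427;
- p = 0.10, same n: 0.0832, 0.0679, 0.0588.

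All six round to the printed table. They concern the primary proportions, which do not use the 7.3.1.2 set, so nothing here changes them.

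**The two sets compared.** Let P be the eyes meeting (1), (2) or (3), and T the eyes with 16-week CSF ≥ 250.
- Criterion (1) requires CSF ≥ 250 at 16 weeks, so every such eye is in T.
- Criterion (2) has no floor, so an eye can be in P and outside T.
- Criterion (3) is settled before treatment, so the 16-week CSF can take any value. An eye now below 250 is in P and outside T.
- An eye at or above 250 with less than a one-unit rise, and no earlier qualifying event, is in T and outside P.

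**Numerical examples.** The protocol does not give the size of a log unit, so a log10 step u is assumed. A one-unit rise multiplies CSF by 10^u and a two-unit rise by 10^(2u). For u = 0.1 the factors are 1.2589 and 1.5849.

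| Eye (CSF in microns) | log10 change | In P? | In T? |
|---|---|---|---|
| 200, then 340 before treatment, 235 at 16 weeks | 0.230 before treatment | yes, by (3) | no |
| 150 to 240, untreated | 0.204 | yes, by (2) | no |
| 245 to 252, untreated | 0.012 (+2.9%) | no | yes |
| 210 to 260, untreated | 0.093 | no | yes |

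**Sensitivity to the step.** A 16-week CSF of exactly 250 fails the one-unit rise if baseline exceeds 250/10^u. A two-unit rise can leave CSF below 250 if baseline is under 250/10^(2u).

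| u (assumed) | 250 is not progression above baseline | two-unit rise can stay below 250 under baseline |
|---|---|---|
| 0.02 | 238.7 | 228.0 |
| 0.05 | 222.8 | 198.6 |
| 0.10 | 198.6 | 157.7 |

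Eligibility allows any baseline below 250 (section 2.2.2), so the added eyes would come mainly from groups 1c and 1d. At u = 0.1, a 16-week CSF of 250 is not progression for 51 of the 60 integer baselines in the women's uncertain band (190 to 249) and for all 40 in the men's (210 to 249). These are counts of possible values, not of expected eyes.

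The loss of treated progressors does not depend on the step size: whatever u is, criterion (3) ignores the 16-week CSF and 7.3.1.2 does not.

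**Imaging available.** Criterion-(3) eyes have a pre-treatment FA under 4.1. Untreated criterion-(2) eyes below 250 have none, because 4.2 triggers the 16-week FA only at 250 or above. Footnotes b and c name DME treatment only, as does the 4.2 exclusion, while 4.1 names DME or CME. Read literally, an eye treated only for CME might have no pre-treatment FA under the footnotes, and could have a post-treatment one at 16 weeks under 4.2.

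**The case against.** The best defense is that the 250-micron cutoff has a reason. It matches the 16-week FA trigger and is part of the post-surgical CME definition in 4.2. The title can be read as a first filter, so that 7.3.1.2 means progressors with CSF ≥ 250. The analysis is descriptive, and chapter 7 calls itself a framework for a later plan.

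Part of this stands. With the title as a filter, an eye going from 245 to 252 is not admitted, so the inclusion of non-progressors holds only on a literal reading. The same reading still loses treated progressors below 250 and criterion-(2) eyes below 250. The cutoff explains why the latter have no FA, but not why eyes with a mandatory pre-treatment FA go untyped. Choosing among FAs could be left to the SAP; the selection rule, however, is already written here.

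Four stronger inferences are not supported:
- That this analysis alone separates DME from CME. Investigators also classify eyes (4.2), 7.3.3 compares that with the reading center, and the synopsis (1.3 G) lists FA type as a secondary outcome without the 250-micron limit, although 7.3.2 does not repeat it.
- That treated eyes still at 250 or above cannot be typed. Section 7.3.1.2 does not restrict grading to 16-week FAs, so the pre-treatment FA can serve.
- That a given share of events is lost. The protocol gives neither a treatment rate nor a response rate.
- That the trial will report any-cause edema as DME incidence. The operative definitions say edema, and criterion (3) names DME or CME; the fault is in the statement of the objective.

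**Conclusion.** The point holds within those limits. As written, the 7.3.1.2 set is not the set of primary events. It omits treated progressors who are below 250 microns at 16 weeks and criterion-(2) progressors below 250, on either reading of the title. On the literal reading it also adds eyes that did not progress. The resulting type distribution is conditioned on response to discretionary treatment.

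Separately, the DME label in 7.1 and 7.3.1.1 contradicts section 1.2 and an outcome that does not distinguish DME from post-surgical CME.

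The effect is confined to the type distribution and the interpretation of the incidence. The omission of treated progressors needs no numerical assumption. The worked examples for the other two groups assume a log10 step, but some mismatch exists for each of the steps of 0.02, 0.05 and 0.1 tried. It should be corrected before analysis.

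**What to change.** - In 7.3.1.2, define the set as all eyes meeting definition (a) of 7.3.1.1. Use the reading center's grading of the pre-treatment FA where non-topical treatment was given, and of the 16-week FA otherwise.
- Add a 'not typed' category and report its size. It will hold untreated criterion-(2) eyes below 250, which get no FA under 4.2.
- Report eyes with 16-week CSF ≥ 250 that did not progress in a separate line.
- In 7.1 and 7.3.1.1, name the outcome center-involved macular edema, as in 1.2.
- Reconcile the DME-only wording in schedule footnotes b and c and in 4.2 with the DME-or-CME wording in 4.1, so that it is clear which FA each treated eye should have.

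The cost is a change of wording and one added category. Section 4.1 already requires the pre-treatment FAs, no new imaging is needed, and sample size and primary estimates stay as they are.

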### 766 **7.3.1.3 Factors Associated with Outcome**

767 Potential factors associated with the primary outcome (other than the prespecified primary  
768 subgroups in section 7.1) will be evaluated in exploratory analyses to determine if there are any  
769 subgroups in which there appears to be more progression of edema at 16 weeks. Point estimates  
770 and 95% confidence intervals will be provided for these secondary subgroup analyses. Event  
771 rates in different subgroups will be compared using Fisher's Exact Test. The study is not  
772 expected to have sufficient statistical power for definitive conclusions in all subgroups.  
773

774 The subgroups may include but are not limited to those tentatively described below. The  
775 definitions will be reassessed after completion of enrollment to determine if the distributions are  
776 sufficient for analysis:

- 777 • Baseline visual acuity: 69 letters or better, 54-68 letters, 39-53 letters, 38 letters or worse
- 778 • Prior PRP: yes/no
- 779 • Baseline severity of retinopathy based on clinician assessment: microaneurysms only,  
780 mild/moderate NPDR, severe NPDR, PDR
- 781 • History of cataract surgery in fellow eye: yes/no
- 782 • Baseline HbA1c:  $< 8\%$ ,  $\geq 8\%$
- 783 • Age at enrollment: below median/above median
- 784 • Diabetes type: Type 1, Type 2, Uncertain
- 785 • Gender: male/female  
786

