 324 primary outcome (including central subfield thickness, HbA1c, cataract surgery in fellow eye,  
 325 visual acuity, and retinopathy severity on clinical assessment)  
 326

327 Secondary outcomes to be evaluated in each subgroup:

- 328 o Visual acuity
- 329 o OCT measured central subfield thickness
- 330 o Presence of DME/CME/Combination on FAs (graded by Reading Center)
- 331 o Progression of diabetic retinopathy on clinical exam  
 332

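### The exploratory predictor analysis fixes an unadjusted Fisher's exact test on categorised factors and omits baseline central subfield thickness from its list, so factors related to thickness, notably sex, can be confounded

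*Protocol*

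**What the plan says.** Section 7.3.1.3 of the protocol covers factors associated with the primary outcome, other than the section 7.1 subgroups. It labels the analyses exploratory and promises point estimates with 95% confidence intervals. It then names the comparison: event "rates in different subgroups will be compared using Fisher's Exact Test". No model, stratification or covariate is mentioned, and the text does not say whether the tests are pooled over the section 7.1 subgroups or run within them.

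Eight factors are listed, tentatively and without closing the list. Three are continuous measurements cut into groups: "Baseline visual acuity: 69 letters or better, 54-68 letters, 39-53 letters, 38 letters or worse"; HbA1c at 8%; and "Age at enrollment: below median/above median". Retinopathy severity has four ordered levels. Prior PRP, fellow-eye surgery, diabetes type and sex are categorical by nature.

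The synopsis (section 1.3 G) describes the same analysis as covering baseline factors associated with the "primary outcome (including central subfield thickness, HbA1c, cataract surgery in fellow eye" and others. Central subfield thickness comes first there but does not appear in the 7.3.1.3 list.

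Section 7.3.1.3 also says that its "definitions will be reassessed after completion of enrollment to determine if the distributions are" sufficient, and that the study is not "expected to have sufficient statistical power for definitive conclusions in all subgroups".

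**The concern.** Progression to center-involved edema depends partly on a fixed CSF threshold of 250 microns, the same for both sexes. An eye that starts thicker can need a smaller relative rise to count as an event. Any factor related to baseline thickness can then look like a predictor although it does not influence swelling. Sex is the clearest case, because the protocol's own limits for no center involvement differ by 20 microns between women and men. Section 1.1.4 also reports that post-operative edema may arise mainly in eyes with retinopathy and central thickening already present.

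Separately, cutting acuity, HbA1c and age into groups discards information in an analysis where events are few. Fisher's test also ignores the order of the acuity and retinopathy levels. Section 1.1.5 says the study's findings may help decide whether future trials are warranted, so a false lead or a missed predictor has some cost.

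**Working it through.** **The plan's own figures.** The protocol gives no planning figure for the factor analyses. Its only quantitative planning is the confidence-interval table in section 7.2, and this reproduces with 1.96 × √(p(1−p)/n). For p = 0.05 the half-widths are 0.0604, 0.0493 and 0.0427 at n = 50, 75 and 100. For p = 0.10 they are 0.0832, 0.0679 and 0.0588. All six round to the stated values.

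**How the threshold acts.** The protocol does not give the size of a log unit, so 0.1 log10 is assumed. One unit is then a factor of 10^0.1 = 1.259 and two units a factor of 10^0.2 = 1.585. An event needs either CSF ≥250 with a rise of one unit, or a rise of two units. The rise required from baseline b is:
- b below 250/1.585 = 158: a factor of 1.585 (the two-unit rule applies first)
- b from 158 to 199: a factor of 250/b (the 250 threshold decides)
- b above 250/1.259 = 199: a factor of 1.259 (the one-unit rule decides)

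At the upper edge of no center involvement, a woman near 190 microns needs a rise of 250/190 − 1 = 32%. A man near 210 needs 26%. The same label means a different distance to the event.

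**Size of the sex artefact.** Assumptions, none from the protocol: normal baseline CSF with SD 22; means of 190 (women) and 210 (men), or a gap of 10 microns; the same log10 change in both sexes, with mean 0.01 to 0.02 and SD 0.05 to 0.06.
- 20-micron gap: crude odds ratio 1.54 to 1.63 with no true sex effect.
- 10-micron gap: about 1.3 (separate runs gave 1.2 to 1.4).
- After adjustment for CSF as a linear term: 1.00 to 1.04.
- After adjustment only for thickness group (1a/1b against 1c/1d), 20-micron gap: 1.57 to 1.65, so the artefact stays.

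Under the same assumptions the artefact is about 1.1 within groups 1c/1d and about 3.9 to 6.2 within 1a/1b. The latter sizes depend heavily on the assumptions.

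**Loss from categorising.** Simulation with a normal covariate and about 10% events, comparing Fisher's test on a median split with logistic regression on the continuous value:

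| Log-odds per SD | N=300 | N=500 |
|---|---|---|
| 0.3 | 19% vs 31% | 31% vs 49% |
| 0.4 | 33% vs 53% | 47% vs 72% |
| 0.5 | 48% vs 70–74% | 70–71% vs 90–91% |

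Part of the gap is the conservatism of Fisher's test: with 250 eyes per group and 5% events its actual size is 0.032, and its power for 5% against 10% is 51%.

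**Events available.** 5% × 500 = 25 and 10% × 500 = 50. Section 7.1 has 4 × 2 + 2 = 10 cells, hence nine indicator terms. That is too many for 25 to 50 events.

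**The case against.** The strongest reply is one of scope. The analysis is exploratory, limited power is admitted, the list is open, and chapter 7 calls itself a framework for a later analysis plan. A crude rate comparison does answer whether some subgroups progress more often. All of this stands and limits the importance of the point. It does not remove it, because the section goes beyond leaving the method open: it names one, and its list disagrees with the synopsis.

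Several stronger readings are tempting and are not supported.
- **That the plan ignores baseline thickness.** It does not: the synopsis names CSF as a factor, and the primary subgroups are defined by thickness. What is missing is CSF in the 7.3.1.3 list and CSF as an adjuster.
- **That the results are confounded.** This is a risk, since pooling is not stated. If tests are pooled over two equal strata, a factor with no effect of its own is flagged in 5.5% of trials when it tracks the strata weakly (40% against 60% prevalence, event rates 5% and 10%). With 30% against 70% prevalence and rates of 5% and 30%, it is flagged in 82%. Even the sex artefact would reach significance in only 3% to 16% of trials at N=500. Testing within subgroups would not cure it, however, as the 1a/1b figures show.
- **That all factors lose power.** Only three of the eight are cut continuous measurements, and only age uses a median split.
- **That categories will be redrawn to suit the outcomes.** The stated criterion is the distribution of the factor. With uniform accrual and about 20 weeks from enrollment to outcome (up to 4 to surgery, then 16), the share with outcomes at the end of enrollment would be (26 − 20)/26 = 23% after 6 months and (104 − 20)/104 = 81% after 24 months. The text does not require that outcomes be unseen, and a short statement would settle it.

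**Conclusion.** The point holds in limited form. Section 7.3.1.3 fixes an unadjusted test on categorised factors and omits baseline CSF, which the synopsis names first. Comparisons of factors related to baseline thickness can therefore mislead. For sex the spurious odds ratio is about 1.3 to 1.6, given the assumed baseline means, SD, common log change and 0.1 log10 step; adjustment for continuous CSF largely removes it. For continuous factors the power given up is roughly 12 to 26 percentage points at N=300 and 18 to 25 at N=500, under the effect sizes shown, a linear effect and a median split.

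A reader might infer that the full section 7.1 subgroup should be adjusted for. The figures do not support that: adjusting for thickness group alone leaves the sex artefact in place, and the ten cells cannot be carried by 25 to 50 events. The primary incidence estimates do not depend on this section, so this is a cheap improvement to an exploratory analysis.

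**What to change.** In section 7.3.1.3:
1. Add baseline central subfield thickness to the factor list, to agree with the synopsis.
2. Replace the Fisher comparison by one small logistic model per factor, Firth-penalised if events are sparse, adjusted for continuous baseline CSF. Enter acuity, HbA1c and age as continuous and retinopathy severity as an ordered trend.
3. Do not enter the full section 7.1 subgroup. Use at most one collapsed term, if events allow.
4. Keep the category rates with 95% confidence intervals as description.
5. State that any redefinition of categories is made without sight of outcomes.

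The cost is a change of wording; CSF, acuity, HbA1c, age and retinopathy grade are already collected. The downside is that with about 25 to 50 events each model can carry only one or two adjusters, so confounding by other factors will remain and the results should still be read as exploratory.
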